AIM 3: To explore the relationship between obesity, attitudes (barriers, motivation) towards physical activity, and physical activity levels in a well-characterized longitudinal cohort of older women with UI symptoms. **Hypothesis 3.** Older women with UI view UI severity as a barrier to a high physical activity. Lower physical activity levels (defined as <6.2 MET hours/week) in women with UI impacts on physical performance and is associated with obesity. Physical activity levels will be determined using the Community Healthy Activities Model Program for Seniors questionnaire that reports metabolic equivalent task (MET) hours/week.(6) Questionnaires will assess barriers to and motivations for physical activity.

METHODS AND MEASURES:

Study Design:

We plan a prospective cohort study with an adaptive design based on physical function status. The design will involve tracking the number of women recruited with physical function impairment and those without any functional impairment. We aim to recruit similar numbers of women in each group. If we find unequal numbers, we will adapt our recruitment strategies based on a woman's functional status.

We will compare changes in outcome measures within and between groups after 6 and 12 weeks of PFME. The change in pelvic floor strength/efficiency will be assessed by repeating the pelvic floor PERFECT assessment and will be compared between groups. Changes in UI symptoms, symptom severity, and impact of UI symptoms on quality of life will be determined using standardized measures described above. Data analysis will define associations between changes in PERFECT measures and the change in UI episodes (based on 3-day voiding diary), severity, and type (based on QUID-7), and impact on quality of life (PFIQ-7) within and between groups. Objective measurement of lower-extremity strength will inform the relationship between lower-extremity strength, pelvic floor strength, and UI symptoms at baseline and the 6-week visit. (See Appendix Figure 1 – Study Flow Chart)

Setting:

Study visits will take place at the Sticht Center on Aging in the Geriatric Research Clinic. The study coordinator will meet the participants in the GRC to confirm eligibility, describe the study, answer any questions, and administer written informed consent.

Subject selection criteria:

- **Inclusion criteria:**
 - a) Women, age 70 years or older
 - b) Symptoms of Urinary Incontinence for greater than 6 months

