(Defined by the QUID assessment as having subscale score for stress ≥ 4 , and/or urge score ≥ 6 , and/or total QUID score ≥ 10)
 - c) Willing and able to be compliant with pelvic floor muscle exercise intervention (standard of care) for 12 weeks and to log compliance
 - d) Willing and able to undergo an extensive physical function evaluation
 - e) SPPB ≤ 9 (for any new screens conducted after amendment 12 is approved)
- **Exclusion criteria:**
 - a) Prior surgical intervention for urinary incontinence within the past 12 months
 - b) Hysterectomy within 12 months
 - c) Having primarily nocturia
 - d) Diagnosis of:
 - i) Pelvic Organ Prolapse beyond the hymenal ring
 - ii) Urogenital Fistula
 - iii) Neurogenic Overactive Bladder (associated with a diagnosis of Multiple Sclerosis or Stroke within past 12 months)
 - iv) Incomplete Bladder Emptying/Urinary Retention with PVR >150 ml (measured by bladder scan)
 - e) Wheelchair bound
 - f) Having significant cognitive impairment or dementia
 - g) Unsafe to exercise (severe cardiopulmonary disease)
 - h) Unable/unwilling to provide informed consent
 - i) Determined otherwise ineligible by the principal investigator

Sample Size Estimate:

With 50 women per group (functional impaired and non-impaired) and assuming a drop-off rate of 15% for a two-sided test, we will be able to detect a 20% difference of improvement of UI episodes (assuming a standard deviation of 32%)[40] with at least a power of 80% at 0.05 significance level for Aim 1.

Interventions and Interactions:**Interaction 1: Mailing of Introductory Letters**

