J. Cognitive function will be assessed using the Montreal Cognitive Assessment (MoCA). Mild cognitive impairment will be defined as MoCA score of <26. Severe cognitive impairment will be determined by MoCA score <21.[38]

At the conclusion of the Study Visit 1, participants are given a folder labeled with their study ID. The folder will contain the following:

- Voiding diary (toilet hat should accompany this)
- Pelvic floor muscle exercise compliance log (we explain that this is an observational study, therefore, they should only complete the log reflecting what they actually are able to do at home)
- Copy of informed consent form
- Label indicating the time/day of their next appointment

- Sheet cover insert containing the bladder diary OR questionnaires necessary for the upcoming study visit 2 (bladder diary), study visit 3 and 4 (Questionnaires and bladder dairy)

All assessments will be repeated during the 6- week follow-up visit. Questionnaire based assessments and UI voiding diaries will also be repeated at week 12. (see *Appendix Table 1 – Assessment schedule*)

*We were mailing the questionnaires, but they would invariably reach the participants in time. Therefore, we are modifying our technique to increase compliance with completing the questionnaires and improve the efficiency of study visits.

Study visit 2 (week 2): (20 minutes) This visit will ensure that pelvic floor muscle strength and contractions are being performed and recorded correctly. The PI will assess each participant by performing a digital vaginal exam, to confirm proper isolation of pelvic floor muscles and ability to complete the PFME prescription. The bladder diary will be reviewed, clarified, and collected. A data abstraction form should be completed at this time. The pelvic floor exercise prescription may be modified at this visit, if that occurs, a new document will be provided and the previous prescription will be stored in the participants chart. The PFME compliance log should be reviewed. A brief visit note should be completed to summarize the events.

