- c) **Dropouts:** Participants who drop out will be contacted by the PI or study coordinator to assess why. They will be offered assistance to help facilitate study completion (e.g., transportation to get to appointments). If they are not willing to return, we will ask that they complete 3-day voiding diary and PFME therapy and mail in the diaries and compliance calendars to the study staff in an attempt to ensure that we collect our primary outcome data. If they comply, they will be provided with a \$30 gift card.
- d) **Reproducibility and representativeness of participants to general population:** We plan to recruit from a diverse community of older women, including underserved, underinsured, and insured patients.

We have a mixed ethnic population of black, non-Hispanic white, and Hispanic Americans in the catchment area; the study will reflect the general population (see Human Subjects section).

Human Subjects Protection

Recruitment & Identification of Cohort:

Potential participants will be recruited from the community of patients in the Wake Forest Baptist Health System and those in a database of older adults interested in volunteering for research studies on aging (the VITAL database in our Sticht Center on Aging). We plan to employ 3 specific recruitment approaches:

- 1) The electronic health record will be searched using the Translational Data Warehouse (managed by the Wake Forest Clinical and Translational Science Institute [CTSI]). Women >70 years old with ICD-10 diagnosis codes [R32 (unspecified UI), N39.81 (functional UI), N39.41 (urge UI), N39.46 (mixed UI), and N39.3 (stress UI)] will be identified as having a diagnosis of UI within 6 months of the query. Potential participants will be mailed a letter introducing them to the study, informing them that they may be eligible to participate and will be contacted within 2 weeks by study staff in order to inquire about their interest to participate. We will include the 6-item Questionnaire for Urinary Incontinence Diagnosis (QUID) validated to establish the diagnosis, distinguish UI type, and measure severity of UI in the letter [18]. It is common for women to self-identify the presence of UI symptoms. Interested women will be instructed to call our study coordinator to learn more.

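### The dropout rule asks for the diary and continued exercise together and ties the $30 to complying, so week-6 outcomes may be recovered selectively from dropouts who keep exercising

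*Combined protocol and SAP*

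**What the plan says.** Under Potential Pitfalls and Alternative Solutions, item c (Dropouts), women who drop out are contacted to learn why and are offered help to finish the study. For those who still will not return, "we will ask that they complete 3-day voiding diary and PFME therapy and mail in the diaries and compliance calendars". The stated aim is to secure the primary outcome. Payment follows: "If they comply, they will be provided with a" $30 gift card. The word comply is not defined.

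Four other places bear on this rule:

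- Study visit 3 (week 6) and Study Visit 4 (week 12) give attending women $30 for completing the visit, with no exercise condition.
- Interaction 3 (Study visit 1) explains that the study is observational and, of the exercise log, that "they should only complete the log reflecting what they actually are able to do at home".
- Analytical Plan & Statistical considerations makes the primary analysis an ANCOVA of percentage reduction in weekly UI episodes at week 6, between functionally impaired and unimpaired women. It names no method for missing outcomes and no sensitivity analysis.
- Study Design also plans to relate PERFECT changes to changes in several outcomes, including "impact on quality of life (PFIQ-7) within and between groups". The dropout rule asks for no questionnaires.

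**The concern.** Outcome collection should not depend on whether treatment continued. The study asks how well a prescribed exercise course works in two groups of women, and women who are given the prescription and then stop belong to that question. A woman who left because she could not keep up the exercises is asked for a package that, taken literally, she cannot deliver, and the rule describes neither a request nor a payment for the diary alone. If such women respond less often than dropouts who still exercise, missingness at week 6 becomes related to stopping treatment and so probably to outcome. With no missing-data method in the analysis plan, this rule is the main safeguard for the primary outcome among women who do not come back.

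The payment wording also sits awkwardly with the visit 1 instruction to log only what was actually done, because it can be read as paying for exercise rather than for an honest record.

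**Working it through.** **1. The plan's own figure.** Inputs from Sample Size Estimate: 50 women per group, "assuming a drop-off rate of 15% for a two-sided test", a 20-point difference, SD 32 points, significance level 0.05.

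- Evaluable per group: 50 × 0.85 = 42.5.
- Standard error of the difference: 32 × √(2/42.5) = 6.94.
- Power: Φ(20/6.94 − 1.96) = Φ(0.92) = 82.2% (81.3% by t-test).
- Required: 41 evaluable per group, and 41/0.85 = 48.2, so 49 against the 50 planned.

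The statement "with at least a power of 80% at 0.05 significance level for Aim 1" is reproduced. It treats the 15% as lost numbers only and makes no allowance for who is lost.

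**2. The two payment rules side by side.** An attending woman completes the visit and is paid, whatever exercise she did. A woman who will not return is asked for diary, exercise and calendars, and is paid if she complies. Exercise enters only the second rule.

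**3. Size, as an illustration.** The documents do not say who drops out, how many dropouts stop exercising, how such women fare, or who would mail a diary. Assume:

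- women who keep exercising improve by 50% if unimpaired (the reduction that Objectives, Aim 2, expects from six weeks of PFME, applied here to this group) and by 50 − 20 = 30% if impaired (the design difference);
- every dropout has stopped, improves 0% and mails nothing;
- the quantity of interest is the gap among all women enrolled.

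With dropout a (unimpaired) and b (impaired), the observed gap is 50 − 30 = 20 and the all-women gap is 50(1 − a) − 30(1 − b). The error, observed minus all-women, is 50a − 30b.

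| a / b (mean 15%) | All-women means | All-women gap | Error in the observed 20 |
|---|---|---|---|
| 15% / 15% | 42.5 and 25.5 | 17.0 | 3 points too large |
| 11.25% / 18.75% | 44.375 and 24.375 | 20.0 | none |
| 5% / 25% | 47.5 and 22.5 | 25.0 | 5 points too small |

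**4. Sensitivity to the shortfall.** More generally, a group's mean is overstated by d × s × g: dropout fraction, share of dropouts who stopped and send nothing, and points by which those women fall short. With d = 15%, s from 0.5 to 1 and g from 25 to 50 (assumed ranges), this is 0.15 × 0.5 × 25 = 1.9 to 0.15 × 1 × 50 = 7.5 points. If d, s and g are the same in both groups, it cancels from the difference. The 3 points in the first row of the table arise only because the assumed shortfall is 50 points in one group and 30 in the other. With the same s and g in both groups but dropout of 20% in impaired and 10% in unimpaired women, the difference shrinks by 0.10 × s × g, or 1.25 to 5 points.

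**The case against.** The strongest reply is that the rule is a request, not a filter. Staff will ask; nothing makes exercise a condition for accepting or analysing a diary, and the declared purpose is to collect the outcome. Comply could mean no more than mailing in the papers. This stands in part. A reader might infer that diaries from non-exercisers are refused or excluded, and the text does not support that. On a plain reading the tie applies to the combined request and the payment. Selective recovery is a risk that follows from the wording, not something the documents show.

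Other stronger readings also fail:

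- That the primary ANCOVA would compare only exercisers. At the assumed 15% drop-off about 85% of women attend, give a diary and are paid whatever they did. The clause reaches only dropouts who also decline to return.
- That the background section shows loss will follow functional group. It links adherence to pelvic floor therapy with weak muscle function. It does not address study dropout or SPPB-defined impairment.
- That a diary filled in on leaving could stand in for week 6. The UI assessment section schedules diaries at weeks 2, 6 and 12, and the primary outcome is fixed at week 6. The dropout rule does not repeat the timing, but the plan points to it.
- That adherence will be over-reported. The visit 1 instruction is to log what was actually done, and a calendar showing little exercise is a valid calendar.

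It is also fair to say that some women who will not return would mail nothing under any wording, so only part of the illustrated error belongs to this sentence. If, say, 30% would answer a reworded request, the attributable part of the 3- and 5-point errors is 0.9 and 1.5 points.

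What survives is that the request is bundled, comply is undefined, and staff could apply it differently from one woman to the next.

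**Conclusion.** The point holds as a matter of wording and risk. The dropout rule combines outcome collection with continued treatment, on a plain reading pays only for both, and offers no diary-only route to a woman who has stopped. Week-6 outcomes may therefore be recovered selectively, and nothing in the analysis plan deals with that.

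No size or direction is established. Under the extreme assumptions in the working, the error in a 20-point gap runs from 3 points too large, through zero, to 5 points too small, depending only on how a 15% average dropout splits between the groups. Those figures show that the result is sensitive to the split; they do not estimate the bias. The sample size statement itself is sound. This is a cheap improvement, not a flaw that undermines the comparison.

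**What to change.** Reword item c so that women who will not return are asked, whether or not they are still exercising, to mail a 3-day diary for week 6 and another for week 12, with a calendar showing what was actually done. Give the $30 for returning the diary, irrespective of exercise. Record whether PFME had stopped and on what date, and state that these diaries enter the primary ANCOVA. Adding the PFIQ-7 and the improvement questions to the mailing is an optional, secondary step.

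The cost is a short amendment, perhaps a few more $30 payments, and some postage. Forms are handed out only for the upcoming visit, so a woman who leaves before week 6 would need the week-12 diary sent to her. Interaction 3 records that the study moved away from mailing questionnaires, so the extra mailing needs some care with timing. No treatment or clinical rule changes.

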Study visit 3 (week 6): (2.5 hours) This visit will take place 6 weeks after initial assessment to assess for changes in pelvic floor strength/function, physical performance, and physical activity. They will bring with them a 3-day voiding diary and 4 weeks of PFME compliance calendars. A subset of assessments from Study Visit 1 will be repeated.(see Table 1) Additionally, self-reported Global Impression of Improvement (GPI), Patient Satisfaction Questionnaire (PSQ), and Estimated Perception of Improvement (EPI) will be assessed using a standardized and validated measure for UI,[39]. To improve recruitment and retention, a \$30 gift card or check will be provided at the completion of this visit.

Study Visit 4 (week 12): (2 hours) To observe long-term adherence to PFME therapy and evaluate the sustained effect on UI symptoms, participants will be asked to return for a visit. They will bring with them a 3-day voiding diary and 6 weeks of PFME compliance calendars. A subset of assessments from Study Visit 1 will be repeated (see Table 1). Additionally, self-reported Global Impression of Improvement (GPI), Patient Satisfaction Questionnaire (PSQ), and Estimated Perception of Improvement (EPI) will be assessed using a standardized and validated measure for UI. [39] We will invite 30 participants (15 with poor physical function defined by SPPB < 9 and 15 with normal physical function defined by SPPB >10) to complete repeated physical performance measures (SPPB, grip strength, postural sway) in order to establish variance among this cohort at 12 weeks. To improve recruitment and retention, a \$30 gift card or check will be provided at the completion of this visit.

Reminder telephone calls: Our study staff will call participants 3 days prior to study visit 2, study visit 3 and 4 to remind them to complete the diary and of the time/date of the appointment. In addition, compliance calls will be made in between study visits 3 and 4 every 2 weeks to check on adherence to the PFME prescription, remind participants of upcoming visits, and review expected completed documentation.

Data Entry:

Outcome measures:

Pelvic floor assessment	

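### The mail-in request to women who will not return leaves out the self-completed questionnaires, so planned secondary self-report outcomes are not requested once a woman has left

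*Combined protocol and SAP*

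**What the plan says.** All references are to the combined protocol and SAP.

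- **Dropout path** (Potential Pitfalls and Alternative Solutions, item c). Staff contact the woman to learn why she left and offer practical help, such as transport, so that she can finish. If she still will not return, she is asked to keep up the diary and exercises and to "mail in the diaries and compliance calendars to the study staff in an attempt to ensure that we collect our primary outcome data". No questionnaire is named.
- **Planned self-report outcomes** (Study Design). "Changes in UI symptoms, symptom severity, and impact of UI symptoms on quality of life will be determined using standardized measures described above". The same section names the QUID for severity and type and the PFIQ-7 for impact, compared both within and between the function groups at 6 and 12 weeks.
- **Improvement and satisfaction** (Study visit 3 and Study Visit 4). At each visit, "self-reported Global Impression of Improvement (GPI), Patient Satisfaction Questionnaire (PSQ), and Estimated Perception of Improvement (EPI) will be assessed". Appendix Table 1 lists the PFDI, the PFIQ and the self-reported improvement measures at weeks 6 and 12.
- **How forms reach participants** (Interaction 3, contents of the folder). The insert for later visits covers "study visit 3 and 4 (Questionnaires and bladder dairy", so questionnaires and diary are already handed out together.
- **Drop-off** (Sample Size Estimate). The calculation is made "assuming a drop-off rate of 15% for a two-sided test" and concerns UI episodes.
- **Missing data** (Analytical Plan & Statistical considerations). No method is given for any outcome.

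**The concern.** The dropout path is built to rescue the diary, and on that it is sensible. A woman who agrees to post a diary has shown that she is reachable and willing to fill in a form, but she is not asked for the other forms that she could complete at home. Examiner-based measures such as the PERFECT assessment cannot be recovered by post. The QUID, PFIQ-7, PFDI-20 and the GPI/PSQ/EPI items can.

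Two things are at stake. First, if women who leave fare differently from women who stay, the self-report results describe a selected group. The exposure here is functional impairment and the follow-up visits last 2 to 2.5 hours on site, so attrition related to the grouping variable is plausible, though the documents give no rates by group. Second, diaries may be recovered for women whose questionnaires are not. The diary and self-report results could then rest on different sets of women, although the Study Design section relates changes in both to the same pelvic floor measures.

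**Working it through.** **1. The plan's own figure.** Inputs from Sample Size Estimate: 50 per group, difference 20 points, SD 32, two-sided 0.05, power at least 80%, drop-off 15%.

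- n per group = 2 × (1.960 + 0.842)² × (32/20)² = 40.2, so 41. Inflated: 41/0.85 = 48.2, so 49, against 50 planned.
- With 50 × 0.85 = 42.5 evaluable per group: 20 / (32 × √(2/42.5)) = 2.88, and power = Φ(2.88 − 1.96) = 82% (81% by noncentral t). With no loss, 88% (87%).

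The stated power is reproduced. It concerns the diary outcome, which the mail-in route protects.

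**2. How many women.** 15% of 100 is 15. If 15% is the total loss by week 12 and none returns a questionnaire, about 85 of 100 are scored at week 12. At week 6 the number lies between 85 and 100, because a woman who leaves after the week-6 visit has already given her week-6 scores. The documents do not say how many leavers would come back with help or how many would reach the mail-in step, so 15 is an upper figure under the plan's allowance.

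**3. Precision.** Detectable difference in SD units at 80% power = 2.80 × √(2/n): 0.56 at n = 50 and 0.61 at n = 42.5. Lost precision is small, so selection is the issue.

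**4. Illustrative bias.** Only the 15% comes from the plan. Every other input is an assumption: 65% of scored women report improvement, a share d of unscored women would have done so, and no leaver is scored.

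| d | Overall shift = 0.15 × (0.65 − d) | Shift in group difference = (0.20 − 0.10) × (0.65 − d) |
|---|---|---|
| 30% | 5.25 points | 3.5 points |
| 40% | 3.75 points | 2.5 points |
| 50% | 2.25 points | 1.5 points |

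- The overall shift compares with SE = √(0.65 × 0.35/85) = 5.2 points, so it is 1.0, 0.7 or 0.4 SE.
- The last column assumes dropout of 20% in impaired and 10% in unimpaired women, leaving 40 and 45 scored. SE of the difference = √(0.65 × 0.35 × (1/40 + 1/45)) = 10.4 points, so the shift is 0.34, 0.24 or 0.14 SE.
- For a change score, if leavers are 0.25 to 1.0 SD worse, the same 20% v 10% split moves the group difference by 0.10 × 0.25 = 0.025 to 0.10 × 1.0 = 0.10 SD.

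Under these assumptions the between-group comparison moves little. A single overall improvement rate could move by up to about one standard error.

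**The case against.** The strongest reply is that the short request is deliberate. The Dropouts item gives its reason, which is to secure the primary outcome, and asking little of a woman who is leaving is a defensible trade-off. The primary analysis is the week-6 diary comparison, and the analytical plan specifies no model for PFIQ, PFDI, GPI, PSQ or EPI. The wider gap is that no missing-data method is stated for any outcome, the diary included. Nor does the folder list name its questionnaires or say clearly when the visit 3 and 4 insert is handed over.

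This has force on priority and size, and it is why the diary must stay first. It does not remove the omission: the Study Design section commits to the QUID and PFIQ-7 comparisons, the two visit descriptions add GPI, PSQ and EPI, and the dropout rule requests none of them.

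A reader might infer more than the documents support:

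- *That these outcomes cannot be scored for women who drop out.* They are self-completed forms that the plan does not request.
- *That all self-report results come from completers only.* Only scores due after a woman leaves are lost. Week-6 scores can already be in hand, and some women may return with help.
- *That the plan forecasts 15 women on this path.* The 15% is a sample-size allowance for UI episodes, not a questionnaire rate or a count of mail-in women.
- *That improvement will be overstated.* It may be. No document gives response rates for leavers.

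**Conclusion.** The point holds as a limited gap in data collection. Self-completed secondary outcomes are not requested from women unwilling to return for any time point after they leave, although questionnaires and diary are already handed out together for visits 3 and 4. At most about 15 of 100 women are affected, if the whole assumed drop-off takes this path, and possibly fewer at week 6. The direction and size of any bias are unknown. The illustrative shifts rest on assumed response rates and an assumed dropout split, and they charge every leaver to the omission, whereas a wider request would recover only those willing to reply. The primary diary outcome and its power are not affected, and nothing here should be read as casting doubt on them. The change is still worth making in advance, because a score not requested at its scheduled week cannot be recovered later by analysis.

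**What to change.** In the Dropouts item, add that women who will not return are also invited to complete and mail the QUID, PFIQ-7, PFDI-20 and the GPI/PSQ/EPI items at the scheduled week 6 and/or week 12. List these after the diary and mark them optional, so that the diary stays the priority. State which forms are supplied and when, since the folder list does not name them.

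Any telephone collection should be timed to those weeks. The call about why she left can fall at any week, and answers taken then should not enter the week-6 or week-12 comparisons.

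Include the returned forms in the planned self-report comparisons, and report the number still missing at each time point by function group. No particular scoring rule for women who remain unscored is needed for this change.

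The cost is a sentence or two in the protocol and a few extra sheets with the mailed diary, with no new visit. The downside is slightly more burden on a woman who is leaving, limited by keeping the forms optional.
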